### **2. Abstract:**

Persons with Parkinson's disease (PD) have impaired mobility, which adversely affects their quality of life. The effectiveness of adapted tango dance, in which participants both lead (internally guide: IG) and follow (externally guide: EG) movement has been demonstrated (Hackney & Earhart 2009, 2010). To improve outcomes in those with PD, the underlying neural mechanisms for both motor impairments and improvement must be investigated. IG and EG movements have distinct neural patterns. Individuals with PD have trouble with IG movement but this problem is helped by strategies employed while "leading". During "following", participants with PD can exploit multiple external cues, which facilitate movement in PD, because EG tasks bypass the basal ganglia (Freedland et al., 2002).

Using a randomized controlled trial design, we will begin with an functional Magnetic Resonance Imaging (fMRI) investigation. We will examine neural correlates of a clinically-used foot-tapping task, during IG and EG conditions in older persons with and without PD. Then, we will assess the relative effectiveness of IG versus EG training used in an adapted tango class, compared to a behavioral control (health education) for improved mobility and foot tapping. Participants with PD will be assessed for disease severity, and will receive tests of outcome measures while "OFF" and "ON" medications, 1 week before training, and 1 week and 1 month after training. Participants must attend 20 lessons of IG or EG adapted tango in 12 weeks, taught by an experienced instructor. In an fMRI scanner, we will assess participants for improved foot tapping after training and investigate changes in activation in specific neural circuits in conjunction with training effects upon mobility.

Our long-term goal is to optimize motor training for persons with PD by understanding lower limb motor circuitry in PD as well as neural changes in circuitry through which training is effective.

### **3. Introduction and Background/Significance**

Impairments in Parkinson's Disease: PD affects 1 million Americans and has formidable personal and socioeconomic costs (>\$34 billion/year) that are increasing. PD cases are expected to double by 2030. PD impacts the VHA health care system with 1.65% prevalence, compared to ~1% in the general population and 50% of these people use VHA as their only source of health care. Persons with PD report 3-4 points lower on the Short-Form 36 physical and mental health-related quality of life (QOL) than those with diabetes, heart disease, and stroke. Because of impaired gait, balance and mobility, people with PD often experience falls which leads to withdrawal from activities, low self-esteem and poor mood. In one study, 70% of PD patients fell within one year and 50% had a repeat fall the next year. Multiple motor symptoms, including postural instability, gait impairment, turning difficulty and dual-tasking problems rob patients of QOL. Turning, gait initiation, and walking through doorways or other tight spaces can trigger freezing, i.e., a stoppage during gait, which affects 53% of patients who have had PD 5 years and more. Adverse changes to gait while dual-tasking are greater in those with PD than those without. Shorter stride length, and slower gait speed while performing a cognitive dual task may result from an underlying cognitive impairment, which is common in PD. A co-morbidity of mild cognitive impairment is associated with greater falls risk in

older people with PD. Spatial cognition, set-switching, executive function and attention are impaired in those with PD, which may affect their mobility. However, exercise programs may improve cognition, reduce rates of “near falling”, and fall incidence in persons with PD.

Treatment of PD Mobility Impairment: Pharmacology and surgery do not fully address the needs of those with PD. Effective motor rehabilitation is necessary, and should be safe, participant-friendly, promote high adherence and have demonstrated efficacy in improving disease severity, mobility and QOL. Traditional exercise programs often suffer from high attrition rates because of high patient task demand and lack of social interaction. Ideally, exercise activities should engage and sustain interest, because 60% of all Americans older than 65 do not achieve recommended daily amounts of physical activity. Activity levels in individuals with PD are even further reduced.

Several mobility programs are effective (e.g., movement strategies, dance, tandem biking, tai chi) for people with PD. Better mechanistic understanding of beneficial exercise effects could improve the design of targeted motor rehabilitation interventions for particular symptoms (e.g., freezing, bradykinesia, and various disease stages of PD). This information would be of great clinical significance to veterans and others with motor impairment of all etiologies, as well as due to PD.

In the last five years, the PI has published a series of studies of training in adapted Argentine-tango (adapted tango) dance showing gains in mobility and balance, maintained one month later in individuals with PD (Hoehn & Yahr stages II-IV). Participant-friendly, adapted tango had low attrition (15%) demonstrating patient acceptance and feasibility with a diverse patient population. In classes, participants alternated between two motor training approaches: a) leading, consisting of internally guiding (IG) movement plans, and b) following, consisting of responding to external guidance (EG). While feasibility and promising outcomes have been demonstrated, previous studies were not designed to make inferences about the causal mechanisms of this intervention. Of interest now is what leading and following, in isolation, contribute to the observed benefits, because evidence shows IG and EG tasks activate distinct neural pathways, which may impact training effects.

Internally and Externally Guided Movement Strategies: Qualities of effective rehabilitative programs are found in both IG and EG training within the context of adapted tango. For example, training for postural instability is most effective if dynamic balance practice and continual adjustment to environmental demands are incorporated. Specifically for individuals with PD, having complex movements broken down into simpler elements by the teacher, done in any dance pedagogy, may facilitate motor performance. Synchronizing movement to rhythm, inherent to dance, may enhance movement speed. A partner may enhance balance as even light touch contact can augment postural control. Nevertheless, there are key differences between IG and EG training that may affect training gains in mobility, as well as the neural circuitry that drives IG and EG movement.

Leading, which uses internally guided cognitive and motor skill, is thought to involve employing a “movement strategy” that demands increased focus on movement plans and mentally rehearsing and/or preparing for movement. Leaders must determine precise spatiotemporal movement parameters of a dance sequence. As such, leading may pose a challenge for individuals with PD, given that they have deficient executive control, specifically in cognitive processes involved in planning and executing complex, goal-directed behavior. However, movement strategies involving strong cognitive involvement and planning are associated with mobility improvements. For example, focusing on critical movement aspects (e.g., longer steps, quicker movements) helps individuals with PD to achieve nearly normal speed and amplitude. Thus, IG training may be helpful for PD patients.

The observed improved function gained via adapted tango in individuals with PD may also be due to the multiple external cues used in this training. Abundant evidence demonstrates benefits of rehabilitative exercise that exploits external cueing and specifically targets neural systems that

support balance. When following (EG training), participants focus on external cues, which may access CTC circuitry and bypass the basal ganglia. External cuing has improved movement initiation. Other research showed that people with PD have faster reaction times when externally cued compared to self-initiated movement. Importantly, during EG partnered movement, such as that engaged during following in adapted tango, the participant is not required to plan precise spatiotemporal parameters of movement (e.g., direction, length of step, timing, and amount of rotation). From moment to moment the follower receives movement guidance from the leader via tactile and, to a lesser extent, visual cues. Because followers are not devoting attentional resources to planning movement, potentially they can attend more to their postural control.

Because of the benefits of both IG and EG training, we will investigate the relative effectiveness of IG (leading) and EG (following) training, within the context of adapted tango, for improved mobility and functional performance in comparison to a behavioral control (health education), in Aim 2. We postulate that mobility gains will be greater in those who participate in IG training if selecting and planning movements is fundamental to gains. However, if training with concentrated external cueing is most effective, we expect to see greater mobility improvements in those who participate in EG training.

Neural Mechanisms of Mobility Training: IG and EG training may impact the neural circuitry that drives IG and EG movement. However, little is known about the neural mechanisms underlying motor and cognitive improvements as a result of rehabilitative training in individuals with PD. A study utilizing positron emission tomography (PET) showed improved vocal intensity after training in the Lee Silverman Voice Training (LSVT®) LOUD program for speech improvement. These motor improvements were correlated with modification in motor, auditory, and prefrontal areas but there was no effect on the basal ganglia. However, in healthy participants, increased activity in the putamen was noted using PET when tango movements were performed to a metered beat. In a related finding, after a week of tango lessons, healthy individuals exhibited increased activity of supplementary motor (SMA) and premotor cortices during imagined walking.

Underlying mechanistic commonalities may exist amongst a variety of therapies that effectively target symptoms of individuals with PD. In the case of deep brain stimulation, stimulating the subthalamic nucleus is thought to suppress abnormal downstream network activity produced by the malfunctioning basal ganglia. If the mechanism of improvement resulting from motor training is similar, there may be a reduction in abnormal neural activity along the STC (putamen, ventral anterolateral thalamus, rostral SMA and primary motor cortex). Alternatively, with effective treatment, there may be enhanced compensatory capabilities within the CTC (cerebellum, ventral posterolateral thalamus, lateral premotor cortex and somatosensory cortex). Another possibility could be increased activity in the basal ganglia, which has been demonstrated to be hypoactive in drug-naïve individuals in early stages of PD.

Neural Mechanisms of Internally and Externally Guided Movement in PD: Knowledge about neural changes that may occur after repeated and targeted training with IG and EG tasks will allow us to develop better rehabilitation training strategies for those with PD. In healthy individuals performing EG finger-tapping tasks, the CTC circuit is primarily recruited, while during IG tasks the STC circuit is primarily recruited. Given that there is dysfunction of the basal ganglia, which is involved in the STC circuit, people with PD have difficulty internally generating movement. PD may influence STC and CTC circuits on a task-specific basis. For example, during EG movements, people with PD activate the CTC network in a way that is very similar to controls; however, in PD patients, both the CTC and STC are activated during IG tasks. In keeping with the idea of increased compensatory activity/connectivity of cerebellar circuits during IG tasks, striato-cortical and striato-cerebellar connections are weaker in individuals with PD than in controls, while cortico-cerebellar connections

are strengthened. As a compensatory response, those with PD tend to recruit the CTC circuit to perform IG tasks increasingly with time.

Studies investigating IG and EG movement typically have examined finger-tapping tasks. Studies that clarify mechanisms of lower limb control are rare. There are differences in the brain functional anatomy between hand and foot movements. Therefore, to understand the mechanisms underlying impairments and training effects in whole-body balance and mobility tasks, lower limb neural activity must be investigated within the context of IG and EG tasks in individuals with and without PD. Thus we will employ foot-tapping, a task that is used in clinical practice to assess lower limb motor control, and also a task that has been adapted to functional neuroimaging. In Aim 1, we will investigate and identify neural correlates of performing a foot-tapping task in participants with PD, compared to age-matched controls. This will allow us to examine the neural circuitry involved in lower limb motor control in persons with PD. Keele et al. (1985) demonstrated that finger-tapping, forefoot-tapping and heel-tapping are highly correlated, suggesting a common underlying mechanism. Therefore, in keeping with studies employing finger-tapping, we hypothesize that IG and EG lower limb control will be associated with activation of the STC and CTC circuits, respectively, in healthy controls. But, those with PD will activate both the STC and CTC circuits during IG tasks, and only the CTC circuit during the EG task. Information gained from the achievement of Aim 1 will further the knowledge base of the pathophysiology of lower limb control in those with PD.

We will use the information gained in Aim 1 about circuits involved in IG and EG movement to evaluate the effects of targeted training upon those same circuits in a clinical intervention we will test in Aim 2. Importantly, Aim 2 proposes to verify if functional improvement noted on foot-tapping and other mobility measures after IG and EG training is related to changes in the activity of IG and EG neural networks. We will also investigate the resting state functional connectivity (RSfc) of these circuits before and after training, because neural networks are best defined in terms of the structure of temporal interactions between regions. The resting state represents the intrinsic blood oxygen level dependent (BOLD) fluctuations of neural areas. Studying connectivity during resting state provides information related to hemodynamic consequences of slow variations in transient neuronal dynamics. These intrinsic fluctuations have a huge metabolic load, are likely functionally relevant and might be used as a marker of network dysfunction. Persons with PD have altered RSfc in motor areas. Examining RSfc of circuits before and after targeted motor training may provide information about the pathophysiology of the disease and its training response. Information gained from Aim 2 will provide bases for recommendations of specific motor strategies within a PD rehabilitative program.

## Significance

In 2003, the Under Secretary for Health, Department of VA, [name], stated that veterans aged 75 and older would increase from 4 to 4.5 million and those over 85 would triple to 1.3 million. The prevalence of PD increases to 4% in the oldest age groups. Veterans with PD have relatively heavy disease burden and nearly 80% will be using VHA as their only source of health care. Clearly, more veterans with PD will need effective and enjoyable rehabilitative modalities that encourage social interaction. Group exercise programs effectively rehabilitate motor impairments, are social in nature and are likely to improve QOL in veterans and others with PD.

Through our series of adapted tango studies, which included veterans from WWII, Korea and Vietnam, we showed evidence for improved mobility, balance and QOL in those with PD. Now we aim to increase our knowledge about the pathophysiology of task-specific mobility impairments, specific types of motor training effects and associated changes in brain activity. With information about the relative effectiveness of leading and following in tango training we will know: 1) if there is evidence that either leading or following movement is superior, 2) preliminary evidence related to the effects of each training on executive function, procedural learning and spatial cognition, and 3) neural

structures and pathways that are accessed by each form of training. Another novel aspect is that we will evaluate neural activity of lower limb movements during EG and IG tasks, which is not well understood, nor has it previously been investigated in those with PD.

This work will contribute to generalized motor theories that will impact care and create more efficient motor rehabilitation in these concrete ways: 1) This project is designed to discover general principles related to improving movement, e.g., if the IG group improves more than EG, we will assume such principles extend beyond tango and we would suggest that incorporating planning and initiating movement in mobility intervention may provide greater therapeutic effects. However, if EG improves more than IG, we would suggest cueing during training is essential for benefits. 2) Dance programs for older adults and individuals with PD are growing popular. Clinicians may use positive results from this study to suggest dance as a beneficial avenue for therapy. 3) Increased knowledge about the effects of specific types of motor training on neural circuitry will lead to greater specificity of treatment for individual patients with particular stages of disease and primary symptoms. Also, we will seek to partner with an organization, e.g., the National Parkinson Foundation to develop DVDs and manuals, presenting the training program fundamentals, graded to complexity from which clinicians can extract information relevant to their practice and incorporate as appropriate (<http://www.parkinson.org/Improving-Care/Education>.) Providing mechanistic basis for successful rehabilitative protocols involving exercise will lend greater support for clinical and community use, and may lead to insurance company support. Demonstrating mechanisms of neural circuitry will provide evidence that training may be effective in ways similar to that of pharmacology and surgical devices, e.g., DBS. This project aims to provide enjoyable treatment while investigating neural mechanisms, upon which future clinical recommendations can be made. Clearly this novel work has potential to impact care and QOL of individuals with PD.

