first we will use fMRI to investigate neural correlates of lower limb control with a foot-tapping task under IG and EG conditions in veterans with and without PD (Aim 1). Imaging studies have previously employed foot-tapping, which is used clinically to assess lower limb control. To achieve Aim 2, we will 1) evaluate the relative effectiveness of practicing IG movement (leading) versus practicing EG movement (following) versus a behavioral control (health education) for improved mobility and lower limb control, and 2) assess neural activity changes underlying improvements in lower limb control across training groups. The long-term goal is to optimize motor rehabilitative interventions for veterans with PD and understand the neural mechanisms through which the training is effective in order to further improve rehabilitation strategies for this and similar diseases.

**Specific Aim 1: Determine neural correlates of internally guided and externally guided foot-tapping in individuals with and without PD.**

**Hypothesis 1:** In healthy controls, IG and EG foot-tapping are related to task-specific neural networks of the striato-thalamo-cortical and cerebello-thalamo-cortical circuits, respectively. In those with PD relative to controls, IG foot-tapping will result in increased activation of both the STC (posterosuperior putamen, ventral anterolateral thalamus, rostral supplementary motor area, primary motor cortex) and the CTC (cerebellum (Larsell lobules IV, V, and VI), ventral posterolateral thalamus, primary somatosensory cortex, ventral premotor cortex) circuits. EG foot-tapping will result in increased activation in the CTC circuit only.

**Specific Aim 2: Determine the effect, in individuals with PD, of internally guided versus externally guided training compared to a behavioral control on: 1) mobility, and 2) whether improved mobility and foot-tapping performance after training correlate with changes in activation and resting-state functional connectivity patterns in IG and EG foot-tapping networks.**

**Hypothesis 1:** If mobility gains are related to training in planning and selecting movements, then those in IG will demonstrate greater improvements than those in EG or control. If mobility gains are related to exploiting cues during training, then those in EG will demonstrate greater improvements than those in IG or control.

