Sensory impairment: To screen for sensory impairments that could affect movement, we will screen for peripheral neuropathy, vision and hearing. We will screen for **peripheral neuropathy** with the 5.07-10g Semmes Weinstein monofilament method and the vibration on-off method in a clean open space, using established criteria. Participants will be screened for best corrected/aided **visual acuity** better than 20/70 in the better eye (World Health Organization International Classification of Disease-10, 2006); Measurement will be performed with intake screening & chart review. [name] will administer the Early Treatment in Diabetic Retinopathy Study Acuity test. Given the role that auditory cues will play in both evaluation (scanning will employ an auditory cue) and treatment (tango dance employs music), we will also screen participants for adequate **hearing**.

Depression: Participants will be screened for untreated depression with the BDI-II, recommended by the American Academy of Neurology, and suitable for screening individuals with PD. A cutoff of 18 is reliable for distinguishing individuals with PD with significant depression. If participants are excluded for depression, but then receive treatment, they may be rescreened and considered for study recruitment.

Ongoing screening for fMRI: Participants will be screened with standard procedures for fMRI eligibility during an initial telephone screen. Then, before every scanning session, participants will answer a standard questionnaire to insure safety during the procedures and adherence to fMRI inclusion and exclusion criteria. Participants will be evaluated for disease severity with the MDS-UPDRS at the beginning of all evaluations.

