For ~20 minutes, participants will perform IG and EG sequences of foot-tapping movements inside the scanner using established methods . As such, the task will involve unilateral ankle dorsiflexion, to a maximum of 30° in a wooden apparatus with movements blocked by IG or EG condition. Participants will be provided foam padding and towels to restrain head motion. Participants’ knees will be flexed to approximately 135° with a soft roll under the knees. An assistant will verify task performance timing and amplitude, as well as monitor for synkinesia from the other limb. If the patient is unable to keep the other limb still, the data will be excluded. Based on pilot scans that we recently collected in 15 individuals with stage II and III PD, we expect 20% attrition for excessive head movement. However, these participants were scanned while ON meds, which generally increases the presence of dyskinesia. Because we will a) test participants OFF meds, b) screen for excessive head and lower limb tremor, and c) target recruitment in order to account for 20% attrition, we expect to retain a sample size that will allow us to detect effects and make meaningful comparisons. Ankle range of motion will be recorded with an MR-compatible potentiometer and amplitude will be averaged over each condition. Absolute timing error will be determined by the potentiometer also, by comparing the timing of every other change in acceleration, with the ideal timing sequence. Thus, the time course of changes in acceleration will be effectively considered the timing of the participants’ taps. Error will be averaged from the accumulated absolute value of the tapping errors which either over- or under-shoot the ideal timing. Tapping will occur at a frequency of 0.5 - 2 Hz, *IRB 60613 Motor Training in PD*

Activation paradigm: In 30 s EG blocks, participants will tap their feet in response to externally provided auditory cues. In 30s IG blocks, participants will tap their feet in pre-learned rhythms. 21 s of rest will occur between IG and EG blocks. There will be 5 blocks per condition

given that individuals with PD demonstrate marked tapping performance deterioration above 2 Hz, in terms of increased movement rate, decreased amplitude and loss of movement phase.

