**Adapted tango:** Composed of simple steps, tango involves frequent movement initiation and cessation, multi-directional perturbations and varied rhythms. Participants focus on trunk control and stepping strategies, coordination, somatosensory awareness, attention to partner, path of movement, and aesthetics. Sessions will begin with a typical dance class warm-up consisting of breathing, limbering and postural alignment to upbeat music. Novel step elements will be introduced every class period. Those with PD will partner with an individual without PD. After novel step introduction, the instructor will present rhythmic training, which is indispensable to partnered dancing. Participants will learn 'typical' rhythms from tango and Latin dances, based upon the system of quicks (Q) and slows (S), ubiquitously used in ballroom dance training to understand the temporal relationship of movement to music. Two quick beats equal one slow beat. Accompanying new rhythms to simple moves first allows transfer of the rhythm to more complex steps. Thus, the instructor will physically introduce rhythms by having participants clap, then tap a foot, then march in place and then walk to the rhythm.

In the last third of class, the new step of the day will be reviewed and added on to previously learned steps. We will maintain manageable class sizes (e.g., no more than 10 pairs of participants with PD and partners) to maximize safety. Participants will dance with new partners (without PD) every 10 minutes, a widely practiced method designed to enhance learning in partnered dance lessons. Steps will be performed in an adaptation of the traditional ballroom frame, holding each other's bent elbows, maintaining forearms parallel to the floor. During the 20 classes, participants will be randomized to either IG or EG roles, i.e., to leading or to following. Leaders (randomized to IG group) will always dance as leaders, and followers (randomized to EG group) as followers.

Those in IG training will choose direction, timing and amplitude of each successive step. Those in EG will learn to attend to sensory cues for movement direction, timing and amplitude of steps, communicated from their partner to them via the frame and center of mass. Choreographic biomechanical patterns will be very similar between IG and EG training. The only difference between leading and following will be whether or not external guidance of movement is provided, after steps are learned.

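### If following (EG) beats leading (IG), the plan would call cueing essential, but both tango arms share music, rhythm and partner contact, and superiority over IG does not show necessity

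*Combined protocol and SAP*

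**What the plan says.** The Significance section plans a general conclusion for each direction of the IG–EG result. If IG wins, it would suggest only that building planning and initiation into mobility training may help more. If EG wins, the claim is one of necessity: "if EG improves more than IG, we would suggest cueing during training is essential for benefits".

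The section on the intervention describes one class format for both roles: a warm-up to music, rhythms taught by the instructor, and a partner held in the same elbow frame. It then says: "The only difference between leading and following will be whether or not external guidance of movement is provided, after steps are learned". Leaders choose the direction, timing and size of each step; followers take these from the partner.

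Other sections confirm the shared elements.
- Screening justifies the hearing test this way: "Given the role that auditory cues will play in both evaluation (scanning will employ an auditory cue) and treatment (tango dance employs music". It draws no distinction between arms.
- The description of the IG and EG foot-tapping tasks says that similar rhythms are learned in both trainings.
- The Introduction states: "Qualities of effective rehabilitative programs are found in both IG and EG training within the context of adapted tango". Among its examples are "Synchronizing movement to rhythm, inherent to dance, may enhance movement speed" and "A partner may enhance balance as even light touch contact can augment postural control".

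The behavioral control is health education, without dance.

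**The concern.** To call cueing essential, one needs to know what happens when it is absent and the rest of the training is kept. No arm provides that. The losing arm in the planned inference would itself have trained with music, rhythm and a partner. A true advantage of being led would then be reported as proof that cueing in general is indispensable.

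The sentence matters beyond its place in the document. The same section says the project is meant to find general principles of movement training and foresees teaching materials for clinicians. The Introduction says Aim 2 will give a basis for recommending particular motor strategies. The Potential Pitfalls section does not mention the shared elements.

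**Working it through.** **Step 1. What each arm receives** (Introduction; Screening; IG and EG foot-tapping tasks; Adapted tango; Behavioral Control Condition)

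| Element | EG | IG | Control |
|---|---|---|---|
| Dance training | yes | yes | no |
| Music | yes | yes | not described |
| Instructor-taught rhythms | yes | yes | no |
| Partner contact in the frame | yes | yes | no |
| Partner guides direction, timing and size of steps | yes | no | no |
| Participant plans and selects steps | no | yes | no |

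- EG versus IG: the last two rows change together, in opposite directions. This is a substitution, not guidance added to an otherwise identical arm. The Introduction itself offers a second route to an EG advantage: followers, relieved of planning, may have more attention for posture.
- EG or IG versus control: dance itself changes along with everything else.
- No pair of arms differs in cueing alone.

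**Step 2. The plan's own figure for the contrast.** Power Analyses for Aim 2 gives a post hoc between-group sensitivity of d = 0.90 with 21 per group, power 0.80 and alpha 0.05. Assume a two-sided, unadjusted two-sample t-test.
- Noncentrality = d × √(n/2) = 0.90 × √10.5 = 2.92, with 40 degrees of freedom.
- Power = 0.812; the smallest d detectable at 80% power is 0.886. The stated figure reproduces. The point does not depend on it.

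**Step 3. Superiority is not necessity.** The effects below are assumptions, in SD units against control, with 21 per group and 20,000 simulated trials each. The EG–IG difference is 0.9 in every row.

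| EG | IG | Chance of significant EG > IG | Chance of significant IG > control |
|---|---|---|---|
| 0.9 | 0 | 0.81 | 0.03 |
| 1.3 | 0.4 | 0.81 | 0.24 |
| 1.8 | 0.9 | 0.81 | 0.81 |

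The same positive EG–IG test is equally likely when leaders gain nothing and when they gain 0.9 SD. The Significance sentence sets no condition on IG versus control.

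**Step 4. What IG versus control could add.** With a true IG benefit of 0.4 SD, that comparison is significant in only about a quarter of trials, so non-significance would not show that IG has no benefit. The 95% interval has a half-width of about 2.02 × √(2/21) = 0.62 SD. The estimate and interval are what inform the question. Even a clear null there would concern leading as taught, music and rhythm included, not uncued training.

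**The case against.** The sentence is an example in a background section, worded as a suggestion. It appears in no hypothesis and nowhere in the statistical analysis plan, and no endpoint, test or sample size depends on it. In context, cueing could mean the partner's guidance, which the Introduction describes as mainly tactile; there the EG expectation is one of degree. The plan also states openly that the two roles share helpful features. Music in class is mentioned explicitly only for the warm-up, and light touch is presented as a postural aid rather than a movement cue.

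Most of this stands and limits the point. It does not rescue the claim of necessity. Even if cueing means partner guidance alone, EG beating IG shows that following did better than leading, not that benefit requires guidance.

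A reader might infer more than the documents support:
- *Hypothesis 1 of Aim 2 is invalid.* It says: "If mobility gains are related to exploiting cues during training, then those in EG will demonstrate greater improvements than those in IG or control". As a prediction about relative gains, the EG–IG contrast can address it.
- *A tie would be read as cueing being unimportant.* Potential Pitfalls says instead that patients and providers would be offered a choice.
- *A null in the scanner would count against EG training.* In the EG scanning condition "participants will tap their feet in response to externally provided auditory cues", and auditory rhythm is common to both tango arms. But no section says a null would be read that way, and foot-tapping is presented as a view of circuitry, not a copy of partner guidance.
- *IG is presented as an uncued arm.* The plan nowhere says so.

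**Conclusion.** The point holds, limited to the one planned conclusion in Significance. EG beating IG would support only that following a partner does better than planning and leading, within music- and rhythm-based partnered dance. It would not show that cueing is essential, for two separate reasons: no contrast isolates cueing, and superiority over IG leaves open how much IG itself helps.

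The first reason rests on the arm descriptions and needs no figure. The second is logical; the simulated probabilities only illustrate it and depend on assumed normal data, equal SDs, 21 evaluable per group and the effects chosen. The consequence is over-interpretation of a result. The randomised comparison and its planned analysis are unaffected. It should be corrected because the sentence would mislead if followed, and correcting it is easy.

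**What to change.** In Significance, rewrite the EG branch to match the strength of the IG branch and remove the word essential. For example: *should EG outperform IG, our suggestion would be that following a partner's guidance, rather than planning and leading, within music- and rhythm-based partnered dance may yield larger therapeutic gains.*

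Add two sentences:
1. The EG–IG contrast cannot separate the presence of guidance from the lighter planning load.
2. Any statement on whether guidance is needed for benefit must also rest on IG versus control, reported as an estimate with its confidence interval.

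Hypotheses 1 and 2 of Aim 2 need no change. Classes, scans, sample size and tests stay as they are. The cost is a narrower claim than the plan now makes.
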